9.2.3 Assessment of other outcomes of interest in a subset of participants

The following other outcomes of interest will only be collected at participating study centres and therefore will only be collected from a subset of trial participants.

- Linezolid trough plasma concentration at day 4 or 5
- Linezolid minimal inhibitory concentration of the respective *S. aureus* strain from the blood

Measurement of linezolid trough levels is an established assay that is routinely performed by the USB diagnostic laboratory and can be ordered from the standard catalogue of analyses. The laboratory will perform linezolid trough analyses in batches on plasma samples collect and frozen by the participating centres (see 9.3.10 *Measurement of trough levels of linezolid in a subset of participants (day 4-5)*).

For the same participants, the minimal inhibitory concentration (MIC, in mg/l) of linezolid for the respective *S. aureus* strain will be measured according to microbiological standard procedures used for clinical routine. In general, this will be done by the gradient diffusion method (Etest).¹¹⁴

9.2.4 Assessment of safety outcomes

9.2.4.1 Adverse events

Adverse events that will be documented by the local investigator or a delegated physician are the following:

Adverse events of special interest:

- Clinical signs of serotonin toxicity until day 7

Serotonin toxicity will be assessed during clinical routine. In case of clinical signs of serotonin toxicity, the Hunter criteria and diagnostic algorithm will be used (including spontaneous or inducible clonus, ocular clonus, tremor, hypertonia and hyperthermia, agitation or diaphoresis, hyperreflexia). Written instructions on how to assess the hunter criteria (only in case of clinical suspicion of serotonin toxicity) are provided in the appendix, chapter 18.2 *The Hunter Serotonin Toxicity Criteria: for diagnosing serotonin syndrome*.

- Laboratory signs of myelosuppression until day 7

Participants will be monitored for signs of myelosuppression (thrombocytopenia, anaemia, leukopenia) as part of the clinical routine blood sampling and graded according to the Common Terminology Criteria for Adverse Events (CTCAE) of the US National Institute of Health/National Cancer Institute.¹¹⁵ This includes for thrombocytopenia grade 1: platelet between lower limit of normal – 75 x 10⁹/L, grade 2: 75 – 50 x 10⁹/L, grade 3: 50-25 x 10⁹/L, grade 4, < 25 x 10⁹/L; for anaemia: grade 1: haemoglobin between lower limit of normal – 100 g/l, grade 2: < 100-80 g/l, grade 3: < 80 g/l, grade 4: life-threatening consequences; urgent intervention indicated, grade 5: death; and for leukopenia: grade 1 leukocytes between lower limit of normal – 3.0 x 10⁹/L, grade 2: < 3.0 – 2.0 x 10⁹/L, grade 3: < 2.0 – 1.0 x 10⁹/L, grade 4: < 1.0 x 10⁹/L.

- Evidence of hyperlactatemia until day 7

In case of a clinical suspicion of hyperlactatemia, local investigators must collect a blood sample to assess if the lactate level is above the upper norm according to specific laboratory-defined reference ranges. For increased lactate levels, the causality with the study treatment will be assessed (see chapter 10.1.1 *Definition and assessment of (serious) adverse events and other safety related events*).

- Acute kidney injury until day 14

Acute kidney injury according to the modified Kidney Disease Improving Global Outcomes (KDIGO) stage 1 is defined as an increase in serum creatinine of $\geq 26.5 \mu\text{mol/L}$ from randomisation (baseline) to study day 5 or an increase in serum creatinine by 1.5 times or more the level of randomisation within 14 days of

randomisation. To collect this outcome, the serum creatinine at baseline (on randomisation day 1 or the calendar day prior to randomisation), day 5 (± 1 day), and only if participant remains hospitalised, at day 14 (± 3 days) will be documented in the eCRF. The values will be captured from available data in the hospital information system or from the participant's primary care physician, respectively.

- *C. difficile*-associated diarrhoea within 90 days.

The treating clinicians will assess for *C. difficile* infection based on the centre-specific diagnostic algorithm if clinical suspicion arises due to diarrhoea during antibiotic treatment. *C. difficile* infection will be evaluated on day 14, at discharge, and on day 90 by reviewing the participant's electronic health records. If a participant reports severe diarrhoea during a 90-day follow-up phone call, occurring after discharge and managed outside the centre, the responsible physician may be contacted to determine if a *C. difficile* infection was diagnosed.

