7. STUDY POPULATION

7.1 Eligibility criteria

Inclusion criteria:

- *S. aureus* grown from at least one blood culture
- Hospitalised at a participating centre
- ≥ 18 years old
- Written informed consent or fulfilling criteria for an emergency exception from informed consent requirements

Exclusion criteria:

- Administration of the initial drug treatment not feasible within 72 hours since the collection of the first positive blood culture with *S. aureus*
- Documented history of positive blood cultures for *S. aureus* occurring between 72 hours and 180 days prior to the eligibility assessment
- Necrotising fasciitis
- Currently receiving linezolid or clindamycin
- Use of any monoamine oxidase A or B inhibitor within the last two weeks
- Known hypersensitivity to linezolid or any other ingredients of the study drugs
- Current severe thrombocytopenia (i.e. $<30 \times 10^9/l$)
- Oral application of study drug not possible (per mouth or per gastric tube)
- Currently breastfeeding
- Local treating team believes that death is imminent and inevitable
- Patient is receiving end of life care and antibiotic treatment is not considered appropriate
- Local treating team believes that participation in the study is not in the best interest of the patient
- Any indication that the patient is unwilling to participate in the study including an advance directive stating such unwillingness

General:

Patients taking serotonergic drugs such as selective serotonin reuptake inhibitors (SSRI) or tricyclic antidepressants are not generally excluded. See detailed information on risk assessment and precautions in chapter 8.6 *Trial specific preventive measures*.

Pregnant women will not be excluded from study participation per se, as linezolid is not formally contraindicated during pregnancy. Limited data exist on the treatment of pregnant women with linezolid, mainly from clinical trials in treating multidrug-resistant tuberculosis. In 31 pregnancies under linezolid exposure, none reported foetal toxicity.⁹⁵ In the event of pregnancy, the treating physician and the patient (or the patient's next of kin) will assess whether the potential benefits outweigh the potential risks to the foetus.

Linezolid has been shown to pass into breast milk and accordingly, breastfeeding should be discontinued prior to and throughout administration of linezolid.

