8.6 Trial specific preventive measures

Thrombocytopenia is a common adverse event of linezolid, but it is usually associated with treatment durations of 10 or more days. Given the lifespan of thrombocytes and the short intervention duration of five days in our study, we expect a low risk of linezolid-mediated thrombocytopenia. However, thrombocytopenia is also commonly seen in participants undergoing sepsis. If participants develop severe thrombocytopenia during the intervention, the local investigator should assess if this may be associated with the trial medication and decide on stopping or continuing the intervention for this participant.

Linezolid should not be used in patients taking any medicinal product which inhibits monoamine oxidases A or B (e.g. the antidepressant moclobemide or the Parkinson's medications rasagiline and safinamide) or within two weeks of taking any such medicinal product.

For participants taking serotonergic agents, the local investigator should evaluate if pausing the serotonergic medication for the duration of the trial is possible. If not, the local investigator (or delegate) should decide if the participant can be included ensuring that potential signs of serotonin toxicity are monitored for the duration of the study intervention phase, or if the patient should be excluded. On trial days 1-5, clinical observation for signs of serotonin toxicity is required for participants taking any of the following medications: serotonin re-uptake inhibitors, tricyclic antidepressants, serotonin 5-HT1 receptor agonists (triptans), directly and indirectly acting sympathomimetic agents (including the adrenergic bronchodilators, pseudoephedrine and phenylpropanolamine), vasopressive agents (e.g. epinephrine, norepinephrine), dopaminergic agents (e.g. dopamine, dobutamine), pethidine or buspirone.

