9. STUDY ASSESSMENTS

9.1 Study flow chart/ table of study procedures and assessments

Study Schedule

	Screening	Enrolment	Intervention phase					In-Hospital Follow-Up (applicable only if participant remains hospitalised)				Close-out
Time point	0-72h before randomisation		Day 1	Day 2	Day 3	Day 4	Day 5	Day 7	Day 14	Day 28	Discharge day	Day 90
S. aureus positive blood culture	X											
Identification of patient		X										
Eligibility checks		X										
Informed consent		X										
Randomisation			X									
IMP administration			X	X	X	X	X					
Time point	0-72h before randomisation		Day 1 (-1 day)	Day 2	Day 3 (±1 day)	Day 4	Day 5 (±1 day)	Day 7 (±1 day)	Day 14 (±3 days)	Day 28 (±4 days)	Discharge day	Day 90 (±7 days)
Clinical assessments												
Baseline data			X ¹									
SIRS criteria								X				
All-cause mortality								Assessed until day 90				
Clinical failure										X	X	X
Length of hospital stay											X	
Length of ICU stay											X	
Antibiotic and/or surgical treatment												X
Laboratory assessments												
Blood cultures				X			X ²					
Creatinine			X				X			X ³		
CRP			X				X					
ALT and gGT			X				X			X ³		
Blood count (Hb, Tc, Lc)			X		X		X	X				
Linezolid trough conc.							X ⁴					
Microbiological failure										X	X	X
New antibiotic resistance												X
Patient reported outcomes												
Quality of life (SF-36)												X
Return to usual level of function												X
Safety assessments												
Serotonin toxicity, myelosuppression, hyperlactataemia ⁵			X	X	X	X	X	X				
Acute kidney injury ⁵							X		X			
C. difficile-associated diarrhoea ⁵												X
SAE / SAR			Collected until day 90									

Abbreviations: S. aureus – *Staphylococcus aureus*; SAE – Severe Adverse Event; SAR – Severe Adverse Reaction; SIRS - Systemic Inflammatory Response Syndrome; ICU – Intensive Care Unit; CRP – C-Reactive Protein; ALT – Alanine Transaminase; gGT – Gamma-glutamyl Transferase; Hb – Haemoglobin; Tc – Thrombocytes; Lc – Leukocytes; SF-36 – Short Form-36

¹ Baseline data include: date of hospital admission, index blood culture, linezolid susceptibility, ethnicity, vital signs, comorbidities, standard antibiotic treatment, markers of severity (mechanical ventilation, cardiac arrest, use of vasopressors, ICU), injection drug use, mental health diagnosis.

² Assessment of persistent bacteraemia. Only required if day 2 blood culture is positive or recorded if done as part of standard of care.

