9.3.6 Assessment of routine laboratory measurements (day 1-7)

Laboratory assessments at start and during treatment will be part of the clinical routine. Either on the day before or on the day of study treatment start, participants will receive routine blood sampling which includes blood count (Hb, Tc, Lc), measurement of renal function (creatinine) and liver function (ALT, gGT), as well as inflammatory parameter (CRP). The study team will review the blood samples at start and during treatment and will re-order any missing laboratory measurements from the collected blood samples if, in rare cases, the necessary measurements for the study according to the visit plan were not routinely performed. No additional blood should be drawn to assess clinical routine measurements. The blood count should be measured 4 times between day 1 (-1) and day 7 (± 1), creatinine and CRP at least on day 1 and day 5 (± 1), creatinine also on day 14 (± 3) if a participant is still hospitalised.

9.3.7 Subproject *Molecular mechanisms of S. aureus bacteraemia* (day 1 until 48h after the patient's first negative blood culture)

Only for a subgroup of patients included in Basel, Switzerland.

Blood will be used to determine the location of *S. aureus* in the blood (intra- or extracellular).

For this, a maximum of one additional 7.5 ml EDTA tube of blood per day will be collected from day 1 until follow-up blood cultures remain negative for 48 hours.

- For patients who consented to further analysis of *S. aureus* in their blood, blood samples will be collected daily. If no routine blood work is performed on an eligible day, an additional blood draw should be performed to collect the sample.
- For patients enrolled via the confirmation of an independent physician under emergency exception from informed consent requirements, blood samples will only be collected during routine blood drawing.
- For patients who refused consent to further analysis in the blood, no additional blood samples for the subproject will be taken.

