- Laboratory signs of myelosuppression until day 7: Participants will be monitored for signs of myelosuppression (thrombocytopenia, anaemia, leukopenia) as part of the clinical routine blood sampling. If blood count shows signs of myelosuppression, the local investigator will be involved to assess the potential causality between the IMP and the laboratory measurements. The local investigator will then decide if the participant needs to stop the intervention.
- Evidence of hyperlactatemia until day 7: In case of a clinical suspicion of hyperlactatemia, the local investigators must collect a blood sample to assess if the lactate level is above the upper norm according to specific laboratory-defined reference ranges. For increased lactate levels, the causality with the study treatment will be assessed. The local investigator will then decide if the participant needs to stop the intervention.
- Acute kidney injury: the kidney function is measured in the blood (creatinine) regularly as part of the clinical routine. To collect this outcome, the serum creatinine at baseline, on day 5 (± 1), and only if participant remains hospitalised, at day 14 (± 3 days) will be documented. The values will be captured from available data from the hospital information system.
- *C. difficile*-associated diarrhoea within 90 days: The treating clinicians will assess for *C. difficile* infection based on the centre-specific diagnostic algorithm if clinical suspicion arises due to diarrhoea during antibiotic treatment. *C. difficile* infection will be evaluated on day 14, at discharge, and on day 90 by reviewing the participant's electronic health records. If a participant reports severe diarrhoea during a 90-day follow-up phone call, occurring after discharge and managed outside the centre, the responsible physician may be contacted to determine if a *C. difficile* infection was diagnosed.

9.3.12 Assessment of serious adverse events and serious adverse reactions (from enrolment until discharge, and at day 90 ±7)

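### Laboratory myelosuppression is graded on absolute counts with no reference to the day-1 value, which dilutes the by-arm safety comparison

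*Protocol*

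**What the plan says.** Section 9.2.4.1 lists laboratory signs of myelosuppression until day 7 among the adverse events of special interest. Platelets, haemoglobin and leukocytes from routine blood sampling are to be "graded according to the Common Terminology Criteria for Adverse Events (CTCAE". The bands are set on the observed value. For platelets, "grade 1: platelet between lower limit of normal" and 75 x 10^9/L, grade 2 is 75 to 50, grade 3 is 50 to 25, and grade 4 is below 25. Leukocytes follow the same pattern, as does haemoglobin up to grade 3. No band refers to the participant's own starting value.

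The other relevant places are:

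- **Section 7.1** excludes "Current severe thrombocytopenia", defined as below 30 x 10^9/L. It sets no entry limit for haemoglobin or leukocytes.
- **Section 8.6** states that "thrombocytopenia is also commonly seen in participants undergoing sepsis".
- **Section 9.1** has a row for "Serotonin toxicity, myelosuppression, hyperlactataemia" that is marked on days 1 to 5 and day 7.
- **Section 9.3.6** says "The blood count should be measured 4 times between day 1 (-1) and day 7" (±1), so a count from the day of randomisation or the day before is scheduled.
- **Section 9.3.11** says that, if counts are low, "the local investigator will be involved to assess the potential causality between the IMP and the laboratory measurements". The investigator then decides whether study drug must stop.
- **Section 9.2.4.1**, on acute kidney injury, uses change from entry, for example "an increase in serum creatinine by 1.5 times or more the level of randomisation".
- **Section 11.4.5** analyses these outcomes descriptively by arm. It lists laboratory signs of haematotoxicity with a window of 14 days.

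**The concern.** The safety question is whether five days of linezolid lowers blood counts. A grade on the absolute count answers a different one: whether the participant had a low count at some time in the window, for whatever reason and from whatever date. In this population many low counts may be present before the first tablet. They fall equally on both arms on average and say nothing about the drug.

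Two things follow. Low counts present at entry can be tallied as events, which swells both arms. A participant who enters at grade 1 and falls to grade 3 is also not distinguished from one who entered at grade 3 and stayed there. Section 3.7 describes myelosuppression as a common adverse effect of linezolid, so this is a comparison that readers and the DSMB will look for.

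**Working it through.** **Can a participant already meet a grade at entry?** Yes. Set the platelet limit in 7.1 against the bands in 9.2.4.1:

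| Platelets at entry (x 10^9/L) | Eligible on platelets? | Grade at entry |
|---|---|---|
| below 30 | no | 3 or 4 |
| 30 to 50 | yes | 3 |
| 50 to 75 | yes | 2 |
| 75 to lower limit of normal | yes | 1 |

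For haemoglobin and leukocytes any value is eligible.

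**Is there a rule elsewhere that removes them?** There is no baseline, change or worsening rule in 9.2.4.1, 9.3.11 or 11.4.5. The schedule marks myelosuppression from day 1, so a pre-dose count can fall inside the event window.

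**Size of the dilution.** The protocol gives no figure to reproduce, so this is an illustration. The inputs are:

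- *b*, the share with a low count at entry: assumed 20%, 40% or 60%. The documents give no rate. The value can be read for one cell line, or for all three pooled, where it cannot be smaller.
- *p*, new onset among those normal at entry: assumed 10% on placebo and 20% on linezolid, a true ratio of 2.0. The documents give no 5-day rate.
- 303 per arm (section 11.2).
- Every participant who is low at entry is recorded as an event, all grades are pooled, and *b* is the same in both arms.

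The formulas are:

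- Absolute grading: rate = b + (1 - b)p
- New onset per randomised participant: rate = (1 - b)p
- Difference under either: (1 - b)(p linezolid - p placebo)
- Standard error of the difference: square root of [r0(1 - r0) + r1(1 - r1)]/303, where r0 and r1 are the two arms' rates

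At b = 40%, absolute grading gives 0.4 + 0.6 x 0.1 = 46% and 0.4 + 0.6 x 0.2 = 52%. New onset gives 0.6 x 0.1 = 6% and 0.6 x 0.2 = 12%.

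| b | Absolute grading | Ratio | New onset only | Ratio | Difference (both) | SE, absolute | SE, new onset |
|---|---|---|---|---|---|---|---|
| 20% | 28% v 36% | 1.29 | 8% v 16% | 2.0 | 8 points | 3.8 | 2.6 |
| 40% | 46% v 52% | 1.13 | 6% v 12% | 2.0 | 6 points | 4.1 | 2.3 |
| 60% | 64% v 68% | 1.06 | 4% v 8% | 2.0 | 4 points | 3.8 | 1.9 |

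With lower assumed onset of 5% v 10% and b = 20%, absolute grading gives 24% v 28%, a ratio of 1.17.

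The difference is the same under either count. The ratio moves towards 1 for any b above zero, and the difference is estimated less precisely. The new-onset columns contain no worsening among participants already low at entry, so they do not model the whole of the proposed fix. If such worsening differs between arms, a count of any grade does not show it at all.

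**The case against.** The strongest case against is that section 9.2.4.1 gives a grading scale, not a counting rule. It does not say that any low value to day 7 becomes one pooled event. Section 10.1.1 defines an adverse event by its temporal association with the study product, which a low count before the first dose does not naturally satisfy, and 9.3.11 adds a causality review. Rules for new-onset events and shift tables are ordinary analysis-plan content, and section 11.4.1 promises such a plan.

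Part of this stands. The text does not state that low entrants are events; it leaves that open, and investigators may discount old low counts. But neither the general definition nor the causality review says how to count, and the causality review serves the decision on stopping study drug. Sites could differ. The analysis plan is promised only before database closure, whereas the DSMB sees safety summaries after 50 and 200 participants (section 11.4.4), possibly before that plan exists. The protocol also fixes a baseline-relative definition for kidney injury in the same section, so it does not regard such definitions as a matter for later.

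A reader might go further and infer that the grading hides any effect of linezolid, or would let the trial clear the drug of haematological harm. The documents do not support that. The absolute difference from new onset survives, tables by grade could still show a shift to higher grades, and other routes remain. Serious events are collected with causality assessment and DSMB review, and adverse events that lead to discontinuation count in the primary outcome. Nor can the loss be stated as lost power, because section 11.4.5 plans no test.

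**Conclusion.** The point holds as one of dilution and loss of clarity. Absolute grading with no baseline reference can record pre-existing low counts as events in both arms, does not separate out worsening, pulls the by-arm ratio towards 1 and makes the difference noisier.

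The direction follows from the formula and needs only that some participants enter with low counts and are recorded. The size rests on assumed inputs: a doubling from 10% to 20% would appear as a ratio of 1.29, 1.13 or 1.06 with 20%, 40% or 60% low at entry. The protocol expects a low risk of linezolid-related thrombocytopenia over five days (section 8.6), so a true excess may be smaller than assumed, and a small excess is harder to see against a swollen background.

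The outcome is descriptive. The consequence is for the safety comparison and the DSMB summaries; the primary analysis and its error rate are untouched.

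**What to change.** In section 9.2.4.1, define the event for each cell line as a new abnormality, or a worsening of at least one CTCAE grade, relative to the day-1 (-1) count. This follows the principle that the same section already applies to acute kidney injury. In section 11.4.5, add a shift table by arm from baseline grade to worst grade in the window, and use the same table for the DSMB. The absolute grades stay visible there, so nothing is lost.

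In the same edit, reconcile the window: day 7 in sections 5.4, 9.1 and 9.2.4.1 against 14 days in section 11.4.5. Blood counts are scheduled only to day 7 (±1).

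The cost is one sentence, one table and one corrected time frame. The day-1 counts are already scheduled, so no new data are needed. The change concerns only how events are counted and leaves the text on stopping study drug as it is.

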3.7 Risks / Benefits

Risks

The most commonly reported adverse event of linezolid is gastrointestinal intolerance, occurring in approximately 30-40% of patients when linezolid is administered for a longer duration.^{72 73} Within the first 5 days of treatment, gastrointestinal intolerance manifests in approximately 8% leading to early discontinuation in 3%.⁷³ Myelosuppression, which primarily presents as thrombocytopenia, is another common adverse effect of linezolid that affects up to a third of patients⁷⁴⁻⁷⁷ and occurs more frequently during treatment durations of ≥ 10 days.^{74 78} Moreover, linezolid is a weak, reversible, and unselective monoamine oxidase inhibitor.⁷⁹ Consequently, the combination of linezolid with other serotonergic drugs, such as selective serotonin reuptake inhibitors (SSRIs) or tricyclic antidepressants, can potentially lead to an increase in serotonin activity. The clinical effects of serotonin excess can range from mild serotonin-related side effects to severe serotonin toxicity.^{80 81} In the largest meta-analysis involving 2208 patients receiving linezolid and 5058 patients not receiving linezolid, the observed incidence of serotonin toxicity was 0.4% among patients taking linezolid in combination with a serotonergic agent (compared to 0.15% in those taking a serotonergic agent alone).⁸² Similarly, in a large cohort of 1135 patients, fewer than 0.5% experienced serotonin toxicity.⁸³ Further, hyperlactataemia is a rare but potentially severe adverse effect of linezolid documented in various case reports.^{72 84 85} The incidence is not well reported, but may be at 1-3% according to retrospective studies.^{73 86} Finally, it should be noted that linezolid can potentially cause peripheral and/or optic neuropathy if treatment is administered for more than 28 days.^{85 87} Given the short treatment duration of 5 days, we expect a low incidence of these adverse events in our study. Nevertheless, we will closely monitor the administration of the drug and, if necessary, terminate treatment in response to adverse events (see 8.6 *Trial specific preventive measures*).

Benefits

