9.2.2 Assessment of secondary outcomes

The secondary outcomes include each part of the DOOR outcome separately as described in chapter 9.2.1 *Assessment of primary outcome* and time to death up to day 90.

Further secondary outcomes will be assessed as follows:

Clinical outcomes:

- Time to being discharged alive (assessed until day 90)

In the eCRF, we collect the day of hospital discharge (see 5.1 *Primary Outcome* for detailed definition of primary outcome). For participants who die during the hospitalisation, 90 days will be recorded.
- Number of days without being on the Intensive Care Unit (ICU) up to day 90 (i.e. mean number of days being alive without being on the ICU between randomisation until day 90).

After day 90 we will collect from the hospital information system data how many days the participant spent on the ICU. Together with the available data on mortality, we will calculate the "Number of days without being on the ICU".

Infection dynamics and control:

Information on these outcomes is collected from the hospital information system data.

- Persistent bacteraemia: positive blood culture on day 5 (± 1 day) after randomisation. If blood culture on day 2 or 3 is negative, then day 5 blood culture will be assumed to be negative (in case it is not carried out).
- Two or more systemic inflammatory response syndrome (SIRS) criteria on day 5 after randomisation. This includes: 1. Abnormal body temperature ($<36^{\circ}\text{C}$ or $>38^{\circ}\text{C}$), 2. tachypnoea or mechanical ventilation (RR >20 breaths per minute), 3. tachycardia (HR >90 beats per minute in an adult), 4. abnormal leukocyte count (from routine blood sampling on day 5 ± 1 day, defined as $>12.0 \times 10^9/\text{L}$ or $<4.0 \times 10^9/\text{L}$ or $>10\%$ of immature (band) forms).
- Change in C-reactive protein (CRP) from randomisation until day 5 (± 1 day). Day 1 CRP means any blood CRP measurement taken on randomisation day 1 or the calendar day prior to randomisation. If there is more than one measurement, the value recorded is the one taken closest before randomisation.
- Early clinical treatment failure between 5 and 13 days after randomisation leading to treatment change. Newly identified focus of *S. aureus* between 14 and 90 days after randomisation as determined by the site investigator. This can incorporate clinical, radiological, microbiological, and pathological findings.

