9.2.4.2 Laboratory parameters

Blood sampling will be done according to clinical routine. Laboratory-specific adverse events will be measured as part of the clinical routine as outlined above. No additional tissue sampling or body fluids are necessary.

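### Hyperlactataemia is counted from any raised lactate to day 7 with no pre-dose lactate listed for collection, so carried-over septic lactate cannot be separated from treatment-emergent cases

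*Protocol*

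**What the plan says.** Section 5.4 and footnote 5 to the schedule in 9.1 make hyperlactataemia an adverse event of special interest until day 7. Sections 9.2.4.1 and 9.3.11 set out how it is found:

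- **Trigger:** "In case of a clinical suspicion of hyperlactatemia".
- **Criterion:** "local investigators must collect a blood sample to assess if the lactate level is above the upper norm", by each laboratory's own reference range. No grade, size of rise or comparison with an earlier value is required.
- **Attribution:** "For increased lactate levels, the causality with the study treatment will be assessed", with reference to the scale in 10.1.1.

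Lactate is absent from the baseline data (9.1 footnote 1, 9.3.4, 9.3.5), from the laboratory rows of the schedule in 9.1, and from the routine panel in 9.3.6, which covers blood count, creatinine, ALT, gGT and CRP. Hyperlactataemia appears in the schedule only as a safety-assessment row.

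Other laboratory outcomes do have a reference value. Acute kidney injury in 9.2.4.1 uses serum creatinine from day 1 or the calendar day before. CRP in 9.2.2 uses the same window: "Day 1 CRP means any blood CRP measurement taken on randomisation day 1 or the calendar day prior to randomisation". Blood counts, used for myelosuppression, have a day 1 value (9.1, 9.3.6).

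On the expected frequency, section 3.7 says: "The incidence is not well reported, but may be at 1-3% according to retrospective studies". It adds that a low incidence is expected with five days of treatment.

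**The concern.** The trial enrols patients with bacteraemia. Some are on ICU, ventilated or on vasopressors, and ICU status is a stratification factor. Sepsis can itself raise lactate. A participant whose lactate was high before the first tablet and is still high on day 2 meets the criterion in the same way as one whose lactate rose on treatment. Nothing the protocol lists for collection separates the two.

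This is more than a detail for the analysis plan. An analysis plan can define treatment-emergent, but it cannot apply the definition to a value that was not collected. What is at stake is how clearly one prespecified linezolid harm can be read in the final safety tables. The primary outcome is not in question here.

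**Working it through.** **Step 1: compare the laboratory-based events of special interest.**

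| Event | Reference value listed | Rule relative to baseline |
|---|---|---|
| Acute kidney injury | Creatinine, day 1 or the day before | Yes (absolute or 1.5-fold rise) |
| Myelosuppression | Blood count, day 1 | Graded; baseline available |
| Hyperlactataemia | None | None |

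Of the three, only lactate has neither a reference value nor a rule relative to baseline.

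**Step 2: inputs for an illustration of size.**

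- Participants per arm, from 11.2: 550 × 1.10 = 605, made even at 606, so 303 per arm. This reproduces the plan's figure from its stated 550.
- Drug effect *e*, from 3.7: 1% to 3%, that is 303 × 0.01 ≈ 3 to 303 × 0.03 ≈ 9 participants. This is a cited range from retrospective studies, not specific to five days, and there is no derivation to check.
- Background *b*, the proportion counted because of sepsis: **not in the protocol**. Assumed at 5%, 10% and 15%, that is about 15, 30 and 45 per arm. A value of 0.5% is added as a near-zero reference, also an assumption.

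**Step 3: formula.** Control rate p0 = b. Linezolid rate p1 = b + e(1 − b), because the drug can add a case only where there would otherwise be none. SE = √[p0(1 − p0)/303 + p1(1 − p1)/303], and the ratio is (p1 − p0)/SE.

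Example with b = 5%, e = 3%: p1 = 0.05 + 0.03 × 0.95 = 0.0785 and the difference is 0.0285. SE = √[(0.0475 + 0.0723)/303] = 0.0199, and 0.0285/0.0199 = 1.43.

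| Assumed background | e = 3%: difference / SE | e = 3%: 95% CI half-width (points) | e = 1%: difference / SE |
|---|---|---|---|
| 0.5% | 2.64 | 2.2 | 1.23 |
| 5% | 1.43 | 3.9 | 0.51 |
| 10% | 1.05 | 5.0 | 0.36 |
| 15% | 0.85 | 5.9 | 0.29 |

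The half-width is 1.96 × SE.

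**Step 4: reading.** At an assumed background of 5% or more, the half-width exceeds the whole 1 to 3 point effect. For a 1% effect the ratio is only 1.23 even with almost no background, so at that end the sample size is limiting whatever the definition.

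**The case against.** The strongest reply is that each raised lactate goes through a causality assessment by blinded staff, on a five-level scale in 10.1.1 that considers timing and other causes. That is a real safeguard. It is weakened, not removed, by the lack of a recorded pre-dose value: timing is the first thing the scale asks about, and the trial data as listed would not show whether the elevation preceded treatment.

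Two further replies stand in full. Allocation is randomised and blinded, so septic lactate falls on both arms alike and does not distort the comparison in one direction. Section 11.4.5 analyses safety descriptively, so ratios to a standard error illustrate precision only.

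A reader might infer more than the protocol supports:

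- **That a pre-dose lactate is itself an event.** No text says so. Assessment starts on day 1, and 10.1.1 ties an adverse event to administration of the product. Only carry-over into the treatment period is open.
- **That the count will mainly reflect sepsis.** The background rate is unknown. Because testing is triggered by suspicion, it could be lower than the range assumed here.
- **That the DSMB would otherwise see the effect.** Its planned looks come after 50 and 200 participants (11.4.4). At about 100 per arm, 1% to 3% is 1 to 3 cases, and even at 0.5% background a 3% effect is only 2.64 × √(100/303) ≈ 1.5 standard errors.
- **That the value is lost for good.** No eCRF is shown, and a lactate measured in routine care remains in the hospital record.
- **That the sampling statements conflict.** Section 9.2.4.2 says "No additional tissue sampling or body fluids are necessary", but it refers back to the measurements described just above it, and the synopsis treats tests ordered on suspicion as routine practice. The two can be read together.

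**Conclusion.** The point holds as a modest gap in data collection. The criterion, the suspicion trigger and the absence of lactate from every baseline and laboratory list are plain in the text, and the contrast with creatinine in the same section shows that a workable alternative is already in use. Carried-over and treatment-emergent elevations cannot be separated from what the protocol lists, and this may obscure a small drug effect.

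How much it obscures cannot be settled from the protocol. The figures of 1.4 and 1.05 standard errors rest on assumed backgrounds of 5% and 10% and on the top of a 1% to 3% range that does not come from five-day courses. Nor should the 2.6 at 0.5% background be read as what the fix would deliver: septic lactates that worsen after the first dose, and those with no pre-dose value, would remain. The gain is a clearer table and a better basis for attribution. It is worth having because it costs little.

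**What to change.** In 9.2.4.1 and 9.3.11, add that two values are taken from existing hospital records where available:

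1. the last lactate before the first dose, from day 1 or the calendar day before (the window already used for creatinine and CRP);
2. the highest lactate after the first dose up to day 7.

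Keep the current count and, in addition, report by arm:

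- participants with a new or worsened value, meaning a post-dose lactate above the local norm and above the pre-dose value;
- a separate row for raised post-dose values with no pre-dose lactate;
- the number of participants tested.

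The cost is a few lines of protocol text and two eCRF fields. Many ward participants will have no pre-dose lactate, so that field will be incomplete and the separate row is needed. Transferring every lactate would be heavy for ICU participants and is unnecessary. No new sample and no change in care is involved.
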